3.2 Dose Escalation

The first portion of the study will evaluate the toxicity profile of talimogene laherparepvec in patients with peritoneal surface dissemination from gastrointestinal, fallopian tube, ovarian, or primary peritoneal tumors.

Using a standard '3+3' dose escalation design, there are up to three dose levels that may be explored. Dose escalation will be dependent on dose-limiting toxicity (DLT) within the cohorts. The following are guidelines for dose escalation:

- Three (3) subjects will be accrued at the starting dose level. Subjects will be monitored for the first cycle (ie. first 5 weeks) before advancement to the next dose level. If no DLTs are seen, 3 subjects may be enrolled to the next dose level.
- If 1 of 3 subjects has a DLT at any dose level, then up to an additional 3 subjects will be enrolled at that dose level. If 1 of 6 subjects experience DLT at a given dose level, then escalation may continue to the next dose level.
- If 2 or more out of 3-6 subjects have DLT in any dose level, then that dose level will be considered to have unacceptable toxicity and the next lower dose level will have additional subjects enrolled to expand to 6 subjects. In this case, the next lower dose level will be declared as the MTD provided no more than 2 of 6 subjects have DLT.
- After the first dose level has completed enrollment, all enrolled subjects will complete at least the first 5 weeks of safety assessments. At that point, the PI, co-PI, and study chair will meet to review safety data for DLTs and determine whether enrollment can proceed at the next dose level. They will notify the funding company of the outcome of the meeting.
- In cases where the only toxicity seen at the lower dose level is Grade \leq 2, re-escalation for intermediate dosing will be considered.

- If there is uncertainty about study drug attribution to DLT, then re-escalation to the next dose level is permitted.
- If $\geq 33\%$ of subjects has DLT at any dose level, then that dose level will be considered to have unacceptable toxicity. The dose level immediately below the one with unacceptable toxicity will be MTD, provided that at least 6 patients have been enrolled to the lower dose level and it was deemed safe.
- If no unacceptable toxicity is seen at the highest dose level, then the highest dose level will be considered the MTD.
- Up to 6 subjects will be enrolled at MTD before proceeding to the Dose Expansion Cohort.
- Once the MTD/RPTD has been determined, the next stage of the study is the Dose Expansion Cohort.

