dose, which all patients will receive). The length of the first cycle is 5 weeks and subsequent cycles are 2 weeks in duration.

In the Dose Escalation Cohort, there will be up to three dose levels explored in a standard '3+3' dose escalation design. Three subjects will be accrued at the starting dose level. If no DLTs are seen at that level, three subjects will be enrolled at the next dose level. If one of three subjects has a DLT at any dose level, an additional three subjects will be enrolled at that dose level. If one of six subjects experience DLT, then escalation may continue. If two or more subjects have DLT at any dose level, then that dose level will be considered to have unacceptable toxicity, the next lower dose level will have additional subjects enrolled. Up to six subjects will be enrolled at the maximum tolerated dose (MTD) before proceeding to the expanded cohort.

The Dose Expansion cohort will enroll subjects at the MTD and follow the treatment scheme described above.

Number of Subjects

The Dose Escalation Cohort will enroll 6 to 18 subjects.

The Dose Expansion Cohort will enroll 6 subjects.

A total of 12 to 24 evaluable subjects will be accrued to assess the safety and tolerability of intraperitoneal talimogene laherparepvec.

Estimated Length of Study Participation

Estimated duration of subject enrollment is 5 months.

Subjects may continue to receive study treatment until they receive up to 4 doses after the initial seroconversion dose, experience unacceptable drug-related toxicity, or disease progression. For subjects that discontinue study treatment with no documented disease progression and no subsequent anti-cancer treatment, they will be followed every 12 weeks or as clinically indicated with tumor evaluations until disease progression or start of new anti-cancer therapy is documented. All subjects will be followed for survival for 1 year after completing treatment.

Study Drug Regimen

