3.3 Dose Expansion Cohort

Once the MTD has been determined, an additional 6 subjects will be enrolled to the dose expansion cohort. All subjects will receive an initial seroconversion dose of talimogene laherparepvec 4×10^6 PFU on Cycle 1 Day 1. Three weeks (+3 days) after the initial seroconversion dose, patients will receive talimogene laherparepvec at the MTD every 2 weeks (± 3 days) for up to 4 doses (in addition to the initial seroconversion dose, which all patients will receive). The length of the first cycle is 5 weeks and the subsequent cycles are 2 weeks in duration. There are a total of four cycles.

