9.1.2 Primary Endpoint

The primary objective of the study is to define the safety and toxicity profile of talimogene laherparepvec in patients with peritoneal surface dissemination from gastrointestinal, fallopian tube, ovarian, or primary peritoneal tumors. The MTD across three dose levels will be determined as described in Table 3.1. The safety analyses will be performed on the safety population, as defined above. Incidence of adverse events occurring in 10% or more of patients will be summarized by Grade, overall and by dose level.

Adverse events will be described using the NCI CTCAE 5.0 criteria. Frequency and severity of adverse events according to the NCI CTCAE v 5.0 body system and severity criteria will be described. In addition, frequency of Grade 3 or 4 adverse events will be described separately. Causality will also be noted.

Laboratory assessments will also be described according to the NCI CTCAE criteria, with separate descriptions for Grade 3 or 4 laboratory abnormalities. Clinically significant laboratory abnormalities will be described as well. Serious adverse events will be summarized, including a causality assessment.

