10.5 Safety Review for Dose Escalation

During the Dose Escalation phase, patients will be enrolled according to a standard '3+3' design. Each subject will have weekly study visits with safety assessments for the first 5 weeks on treatment (cycle 1). Once the first dose level has completed enrollment and completed cycle one, enrollment will be placed on hold and a safety review will be conducted. The PI, co-PI, and study chair will meet and review the safety data for DLTs up to that point. Based on their review, the group will determine whether study enrollment can proceed at the next dose level or the MTD has been reached based on the rules outlined in section 3.2. The PI or designee will inform the funding company of the outcome of the safety review.

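### Section 3.2 allows a backfilled dose level to be named the MTD with 2 DLTs in 6 subjects, a count the protocol elsewhere calls unacceptable

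*Combined protocol and SAP*

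**What the plan says.** The rule in question is the second sentence of the third bullet in Section 3.2. After a level has failed and the one below has been filled to six: "In this case, the next lower dose level will be declared as the MTD provided no more than 2 of 6 subjects have DLT".

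Three other statements set the limit for unacceptable toxicity:

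- The first sentence of that bullet: "If 2 or more out of 3-6 subjects have DLT in any dose level", the level has unacceptable toxicity.
- A later bullet in Section 3.2, for a DLT proportion of 33% or more: "of subjects has DLT at any dose level, then that dose level will be considered to have unacceptable toxicity".
- The Synopsis, under Study Design: "If two or more subjects have DLT at any dose level, then that dose level will be considered to have unacceptable toxicity". It makes no allowance for 2 of 6.

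Section 3.2 also permits escalation after an expansion to six only when 1 of 6 has a DLT.

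Two sections refer to the MTD rule. Section 10.5 has the safety review group decide whether "the MTD has been reached based on the rules outlined in section 3.2". Section 9.1.2 states: "The MTD across three dose levels will be determined as described in Table 3.1". Table 3.1 lists doses and subject numbers and contains no decision rule. Section 3.3 then uses the result: "Once the MTD has been determined, an additional 6 subjects will be enrolled to the dose expansion cohort".

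**The concern.** At 2 DLTs in 6, one bullet both rejects a dose level and names it the MTD. Each of the three rejecting statements applies to any dose level, so a backfilled level is not exempt. A review group that followed Section 3.2 to the letter would have two opposite instructions. It would have to choose between them after seeing the data, just after a higher dose had failed.

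The stake is the dose given to the six expansion subjects. Section 3.3 gives no numerical DLT stopping rule for that cohort, and Section 11.7 mentions toxicity stopping rules without stating any. Section 3.2 also treats the MTD and the recommended phase 2 dose as one decision, so the choice could carry beyond this trial. The adverse-event summaries by dose level in Section 9.1.2 are not affected.

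**Working it through.** **1. The thresholds at six subjects.** 2/6 = 0.333, which is at least 0.33; 1/6 = 0.167, which is below it.

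| DLTs in 6 | Bullet 3, sentence 1 | 33% bullet | Synopsis | Bullet 3, sentence 2 (backfilled level) |
|---|---|---|---|---|
| 0 or 1 | acceptable | acceptable | acceptable | MTD |
| 2 | unacceptable | unacceptable | unacceptable | **MTD** |
| 3 or more | unacceptable | unacceptable | unacceptable | not MTD |

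The rules disagree at one count only, 2 of 6.

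**2. The path that reaches it.** A level with 1 DLT in its first 3 subjects is expanded at once ("If 1 of 3 subjects has a DLT at any dose level, then up to an additional 3 subjects will be enrolled") and has failed if it reaches 2 of 6. That route is unaffected. The conflict needs a level cleared at 0/3, failure of the level above, a backfill with 3 subjects, and exactly 2 DLTs among those 3.

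**3. Effect of the limit once a backfill happens.** The documents give no expected DLT rates, so the true rate p is an assumption. With X ~ Binomial(3, p) among the added subjects:

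- limit 2 of 6: P(accept) = P(X ≤ 2) = 1 − p³
- limit 1 of 6: P(accept) = P(X ≤ 1) = 1 − p³ − 3p²(1 − p)
- P(0/3, then 2 of 3) = (1 − p)³ × 3p²(1 − p)

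| p | Accept, limit 2 of 6 | Accept, limit 1 of 6 | P(0/3, then 2 of 3) |
|---|---|---|---|
| 1/3 | 0.963 | 0.741 | 0.0658 |
| 0.40 | 0.936 | 0.648 | 0.0622 |
| 0.50 | 0.875 | 0.500 | 0.0469 |

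As written, the backfill rejects the level only if all three added subjects have DLTs. The last column is before multiplying by the chance that the level above fails. Its maximum over all p is 0.0658, at p = 1/3.

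**4. Chance of the conflict over the three-level design.** For level i with rate pᵢ:

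- Aᵢ = P(0/3) = (1 − pᵢ)³
- Bᵢ = P(1/3, then 0/3) = 3pᵢ(1 − pᵢ)² × (1 − pᵢ)³
- Rᵢ = P(level fails) = 1 − Aᵢ − Bᵢ
- Tᵢ = P(2 of 3) = 3pᵢ²(1 − pᵢ)

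Conflict at level 2 = (A₁ + B₁) × A₂ × R₃ × T₂. Conflict at level 1 = A₁ × R₂ × T₁.

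For rates 5/10/20%: A₁ = 0.8574, B₁ = 0.1161, A₂ = 0.729, R₂ = 0.0939, R₃ = 0.2914, T₁ = 0.0071, T₂ = 0.027. Level 2: 0.9735 × 0.729 × 0.2914 × 0.027 = 0.0056. Level 1: 0.8574 × 0.0939 × 0.0071 = 0.0006.

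| Assumed DLT rates, levels 1/2/3 | Level 1 | Level 2 | Total |
|---|---|---|---|
| 5/10/20% | 0.0006 | 0.0056 | 0.6% |
| 10/20/40% | 0.0057 | 0.0308 | 3.6% |
| 20/33/50% | 0.0278 | 0.0386 | 6.6% |
| 33/50/60% | 0.0545 | 0.0187 | 7.3% |

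These totals cover the first de-escalation step. The further route, where a backfilled level 2 reaches 3 of 6 and level 1 is then backfilled, adds at most 0.1 percentage point in these scenarios.

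**The case against.** The strongest objection is that the path is rare and probably sits at the low end of the range. Three of the four scenarios assume a top-dose DLT rate of 40% to 60%. Section 10.4.2 reports doses up to 4 mL at 10^8 PFU/mL every 2 weeks without evidence of dose-limiting toxicity. That is 4 × 10^8 PFU, the same as dose level 3. At rates of 2/5/10% the conflict arises in 0.06% of trials, and at 1/2/5% in 0.003%. The 96% versus 74% type of comparison also applies only after a toxic level has passed at 0/3, which has a probability of 30% at p = 1/3 and 12.5% at p = 0.5.

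This bears on how often the problem would arise, and on that it is fair. It is not decisive. The reported experience is not from intraperitoneal dosing, which is the reason for running this trial, and a dose-finding rule has to work when the dose proves more toxic than hoped.

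A second objection is that people decide, not the bullet. Section 3.2 describes its rules as guidelines, the 33% bullet requires the lower level to have been judged safe, and Section 11.7 provides continuous adverse-event monitoring with possible de-escalation or closure. These checks make it less likely that expansion would open automatically at 2 of 6. They do not say which limit applies, and Section 10.5 sends the group back to Section 3.2.

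It could also be said that some 3+3 variants accept 2 of 6 at the MTD. This protocol defines 2 of 6 as unacceptable at any level, so its text contradicts itself under either convention.

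**Conclusion.** The concern holds. The contradiction is in the current text and depends on no assumption: at 2 DLTs in 6 on a backfilled level, one sentence names the MTD and three statements reject the dose. The limit consistent with the rest of the protocol is 1 of 6.

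The chance of meeting the conflict is small, 0.6% to 7.3% over the four assumed rate profiles and lower still if DLTs are very rare. The consequence when it is met is six further subjects treated at a dose the protocol itself rejects. All the probabilities rest on assumed DLT rates and independent subjects. The point should be corrected before the rule is needed, because otherwise the limit would be chosen after the DLTs were seen.

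**What to change.** In the third bullet of Section 3.2, change the limit for the backfilled level from 2 of 6 to 1 of 6. That change alone removes the contradiction.

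Three optional additions would make the rule easier to apply:

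- State that the 33% rule applies only once six evaluable subjects have been treated at a level, or delete it. With no minimum number of subjects, it literally also rejects 1 of 3, although the second bullet and the Synopsis make the intended action clear (enrol three more).
- Give one action per count in a single table that also covers backfilled levels: 0/3 escalate; 1/3 enrol three more; 2 or more of 3 unacceptable, go down; 0 or 1 of 6 acceptable; 2 or more of 6 unacceptable, go down. At level 1 there is no lower dose, so state that enrolment stops and no expansion opens.
- Have the Synopsis, Section 9.1.2 (in place of its pointer to Table 3.1) and Section 10.5 cite that table.

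The cost is protocol wording only, with no added procedures and no change to the planned number of subjects.

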related toxicity (e.g. disease progression or inter-current illness) are considered non-evaluable for DLT. All subjects (in Dose Escalation and Dose Expansion) who are accrued, received study treatment but did not complete initial restaging due to reasons other than disease progression (e.g. inter-current illness) will be considered non-evaluable for efficacy.

Table 3.1 Proposed Dose Levels

Dose Level	No. Evaluable Subjects	TVEC IP, once every 2 weeks x 4 doses*
Dose Escalation		
1 (starting dose)	3-6	4×10^6
2	3-6	4×10^7
3	3-6	4×10^8
Dose Expansion		
Expanded Cohort	6	MTD

*All patients will receive an initial seroconversion dose of 4×10^6 PFU. The first dose at each of these Dose Levels will be administered 3 weeks (+3 days) after the initial seroconversion dose, and then be given every 2 weeks \pm 3 days for a total of 4 doses at each Dose Level (in addition to the initial seroconversion dose, which all patients will receive).

Using a standard '3+3' dose escalation design, there are up to three dose levels that may be explored. See Table 3.1 for the dosing scheme.

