3.2.1 Dose Limiting Toxicity

Toxicity should be evaluated and defined according to CTCAE version 5.0, and should only include events assessed as related to talimogene laherparepvec during treatment and up to 30 days after the last talimogene laherparepvec injection.

The following herpetic events should be considered as DLTs:

- Serious herpetic events such as herpetic encephalitis, encephalomyelitis or disseminated hepatic infection.
- Any herpetic events confirmed due to talimogene laherparepvec that require treatment with acyclovir or similar anti-viral agent. Talimogene laherparepvec treatment should be suspended if treatment is required with systemic acyclovir or other anti-virals. If ongoing anti-viral treatment is required, talimogene laherparepvec treatment should be permanently discontinued.

The following are also considered DLTs:

- Grade 3 or greater immune-mediated adverse events.
- Any grade plasmacytoma at or near the injection site or evidence of impaired wound healing at the injection site.
- Grade 3 or greater allergic reactions considered at least possibly related to talimogene laherparepvec.
- Grade 4 non-hematologic toxicity.
- Grade 3 non-hematologic toxicity lasting > 3 days despite optimal supportive care;
 - Grade 3 fatigue will not be classified as DLT, irrespective of duration.
- Any Grade 3 or higher non-hematologic laboratory value if:
 - Medical intervention is required, or
 - The abnormality leads to hospitalization, or
 - The abnormality persists for > 1 week unless deemed not clinically important per both treating physician and study PI or co-PI.
- Grade 3 or 4 febrile neutropenia.
- Grade 4 thrombocytopenia associated with bleeding event required intervention.
- Any other intolerable toxicity leading to permanent discontinuation of talimogene laherparepvec.
- Grade 5 toxicity (i.e., death).

If an unexpected DLT occurs, talimogene laherparepvec administration should be delayed until the DLT has resolved to at least CTCAE (v. 5.0) Grade 1. If talimogene laherparepvec dosing is delayed by more than 6 weeks from the date of the planned dose due to the occurrence of an adverse event that is

considered related to talimogene laherparepvec, the subject must be permanently taken off talimogene laherparepvec treatment.

Management and dose modifications associated with all adverse events are outlined in Section 7.0.

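### Section 3.2 lets a dose level closed by its own 2-or-more-DLT rule be reopened when attribution is uncertain, without saying how an unresolved event counts

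*Combined protocol and SAP*

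**What the plan says.** Four places in the combined protocol and SAP bear on this.

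- **Section 3.2, closing rules.** One bullet begins "If 2 or more out of 3-6 subjects have DLT in any dose level" and declares such a level unacceptably toxic. The level below is then filled to 6 subjects and becomes the MTD, provided its own DLT count is acceptable. A later bullet applies the same label when 33% or more "of subjects has DLT at any dose level, then that dose level will be considered to have unacceptable toxicity". Neither bullet has an exception for doubtful attribution. The synopsis gives the first rule ("If two or more subjects have DLT at any dose level, then that dose level will be considered to have unacceptable toxicity") and has no re-escalation option.
- **Section 3.2, the permission.** Between those two bullets stands: "If there is uncertainty about study drug attribution to DLT, then re-escalation to the next dose level is permitted". It names no decision-maker, no cohort size and no counting rule.
- **Section 3.2.1, what a DLT is.** Toxicity for this purpose "should only include events assessed as related to talimogene laherparepvec during treatment" and up to 30 days after the last dose. Only allergic reactions carry an explicit lower threshold, "considered at least possibly related to talimogene laherparepvec".
- **Section 10.5, the review.** "Once the first dose level has completed enrollment and completed cycle one, enrollment will be placed on hold", after which the PI, co-PI and study chair review the DLTs. They decide by the Section 3.2 rules.

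**The concern.** Re-escalation presupposes an earlier step down, and in this design a step down follows only from closing a level. The bullet therefore allows a return to a level that the adjacent rule has declared unacceptable. It also speaks of a DLT with uncertain attribution, whereas under Section 3.2.1 an event becomes a DLT only after being assessed as related. The plan does not say what happens when that assessment cannot be settled.

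The stake is the MTD, which Section 9.1.2 places within the primary analysis and Section 3.3 gives to the 6 expansion subjects. Two people applying the text in good faith to the same counts could fix the MTD at the lower level or send new subjects back to a dose ten times higher.

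**Working it through.** The plan states no operating characteristics for its 3+3 rule, so there is no figure of its own to reproduce. The check has two parts.

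**1. The rules applied to the same data.** Inputs: the Section 3.2 rules, and Table 3.1, whose "No. Evaluable Subjects" column allows 3 to 6 per level at 4×10^6, 4×10^7 and 4×10^8 PFU. Assume the subject with the doubted event completed cycle 1 and so stays evaluable.

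| Data at level 2 or 3 | Doubted DLT counted | Doubted DLT not counted |
|---|---|---|
| 2 of 6 | 2/6 = 33.3%: closed, step down | 1/6 = 16.7%: escalate |
| 2 of 3 | 2/3 = 66.7%: closed, step down | 1/3: add up to 3 subjects |

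The text supports either column while attribution is unresolved. If the event is finally judged unrelated, Section 3.2.1 supports the right-hand column. A step down needs a lower level, so only levels 2 and 3 are affected.

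If every DLT is kept and the limit of 6 holds, reopening cannot help the level pass. A level closed at 2 or 3 of 3 ends with at least 2 of 6, and a level closed at 6 has no places left. The added chance of passing is 0. Any effect therefore requires a DLT to leave the count.

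**2. Illustration of size.** Let p be the true DLT rate and r = 1 − p. The documents give no intraperitoneal DLT rate, so p is assumed.

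Plain rule (0 of 3, or 1 of 3 followed by 0 of 3): P = r³ + (3pr²)(r³).

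- p = 0.4: 0.216 + 0.432 × 0.216 = 0.309
- p = 0.5: 0.125 + 0.375 × 0.125 = 0.172

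Assumed set-aside rule: one DLT is dropped in every failure with exactly 2 DLTs, within 6 subjects. This adds (3pr²)² for 2 of 6 read as 1 of 6, and (3p²r)(r³) for 2 of 3 read as 1 of 3 and followed by 0 of 3.

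- p = 0.4: 0.309 + 0.187 + 0.062 = 0.558
- p = 0.5: 0.172 + 0.141 + 0.047 = 0.359 (unrounded terms)

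| True DLT rate | Clears level, all DLTs counted | Clears level, one DLT set aside |
|---|---|---|
| 10% | 0.906 | 0.985 |
| 20% | 0.709 | 0.905 |
| 40% | 0.309 | 0.558 |
| 50% | 0.172 | 0.359 |

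A second assumption gives the same direction. If a share f of DLTs is not counted, p is replaced by p(1 − f). With f = 10% / 25% / 50%, the chance of clearing a level goes from 0.434 to 0.500 / 0.605 / 0.783 at p = 33%, and from 0.172 to 0.234 / 0.351 / 0.600 at p = 50%.

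**The case against.** The strongest reply is that the plan does contain a counting rule. Section 3.2.1 admits only events assessed as related. Section 3.1 makes a subject who misses cycle 1 assessments through progression or intercurrent illness non-evaluable for DLT. This stands. A reader might infer that the plan never allows a doubted event to leave the count, or is silent on attribution altogether; the documents do not support either. The gap is the event that remains unresolved.

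Second, Section 3.2 calls its list guidelines, and the bullet may be a deliberate exception. That is possible, but the text does not say so, and Section 10.5 treats the list as the rules for declaring the MTD. Even as an exception, it leaves the count undefined.

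Third, the 33% rule is a poor benchmark. Read literally, 1 of 3 (33.3%) also meets it, although the list sends 1 of 3 to expansion. This also stands, so the point rests on the 2-or-more rule.

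Fourth, Section 10.5 names a hold only after the first level, and a reader might infer that no review follows levels 2 and 3. Its listed outcomes include having reached the MTD. Section 3.2 does not yield that result from level 1 alone, which suggests that the review was meant to recur. The timing is unclear; a missing review is not shown.

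Finally, discretion has a purpose. Section 1.1 names bowel obstruction as a frequent route to death in these patients, and setting aside a truly disease-related event is correct. At low true rates the bullet would mostly reverse false stops: the plain rule stops 9% of the time at a 10% rate and 29% at 20%. Section 10.4.2 also reports no dose-limiting toxicity in earlier trials at up to 4 mL of 10^8 PFU/mL, so the case may seldom arise. These arguments bear on frequency. They do not settle how an unresolved event should count.

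**Conclusion.** The point holds and should be fixed. A stated permission reopens a level that the 2-or-more rule in the same list has closed, and an unresolved event has no defined place in the count. Identical 2-of-6 or 2-of-3 data can therefore support opposite MTD decisions at doses a factor of ten apart. This conclusion rests on the text alone.

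The probabilities do not have that standing. A reader might infer that the plan raises the chance of clearing a toxic level from 31% to 56%. The documents do not support that: the figure assumes a 40% true rate, a DLT set aside in every failure with exactly two, and that each one set aside was truly caused by the drug. With all DLTs kept and at most 6 per level, the increase is zero. The documents give neither a DLT rate by this route nor the share of events whose attribution would be doubted.

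**What to change.** Replace the re-escalation bullet in Section 3.2, and align Section 10.5, with the following:

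1. The PI, co-PI and study chair settle attribution before every dose decision, including after levels 2 and 3.
2. An event that otherwise meets a DLT criterion, and that the group cannot attribute to another cause, counts as a DLT.
3. A level with 2 or more counted DLTs is not reopened on attribution grounds.
4. Every counted DLT stays in that level's reported DLT rate.

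A general change of the Section 3.2.1 threshold to possible relatedness is not needed; it would be a separate design choice. The synopsis already gives the 2-or-more rule without the re-escalation option and can stand.

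The cost is amendment wording and, if not already held, one meeting of the existing group after each of levels 2 and 3. No visits or data are added. The group loses some discretion, and the MTD may be lower if a disease-related event such as bowel obstruction is counted. A few more cohorts may expand to 6, within the planned 6 to 18 escalation subjects. For example, if the counted rate rose from an assumed 10% to 20%, the chance of exactly 1 of 3 would go from 3(0.1)(0.9²) = 0.243 to 3(0.2)(0.8²) = 0.384. That is 0.141 × 3, or about 0.4 more subjects per level opened.

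### The 33% DLT bullet in Section 3.2 has no minimum denominator, so read literally it rejects a dose level at 1 of 3, the count that the 3+3 rule expands to six

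*Combined protocol and SAP*

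**What the plan says.** The trial uses a standard '3+3' design with up to three dose levels and three to six evaluable subjects per level (Table 3.1). Section 3.2 lists the escalation rules as bullets, and four of them bear on this point:

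- **Expansion at 1 of 3.** "If 1 of 3 subjects has a DLT at any dose level, then up to an additional 3 subjects will be enrolled". The synopsis says the same: "If one of three subjects has a DLT at any dose level, an additional three subjects will be enrolled at that dose level".
- **Escalation at 1 of 6.** "If 1 of 6 subjects experience DLT at a given dose level, then escalation may continue to the next dose level".
- **Count rule.** "If 2 or more out of 3-6 subjects have DLT in any dose level", the level has unacceptable toxicity.
- **Percentage rule.** If 33% or more "of subjects has DLT at any dose level, then that dose level will be considered to have unacceptable toxicity". The level immediately below then becomes the MTD, "provided that at least 6 patients have been enrolled to the lower dose level and it was deemed safe". This six-patient condition applies to the lower level only, not to the level being rejected.

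Under Section 10.5, the PI, co-PI and study chair decide whether to go to the next level or whether "the MTD has been reached based on the rules outlined in section 3.2".

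**The concern.** One DLT in three subjects is the branch point of a 3+3 design: too little to reject the level, too much to escalate, so three more subjects are treated. The percentage bullet, taken at its word, rejects the level at that same count. Section 3.2 therefore gives two verdicts for one outcome, and nothing in 3.2 or 10.5 says which prevails.

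A reviewer who applied the percentage bullet literally would stop at a count where the protocol elsewhere calls for more data, and could carry a lower dose into the six-subject expansion cohort. The starting level is the awkward case, because Table 3.1 has no dose below it to name as the MTD. Section 9.1.2 places MTD determination under the primary endpoint, so the rule that drives it should have one reading.

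**Working it through.** The plan derives no operating characteristics for these rules, so there is no stated figure to reproduce. The check has two parts.

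**1. Where the rules differ.** The inputs from Section 3.2 are the 33% threshold, the count of two or more, and cohorts of three to six. For each n, this is the smallest number of DLTs that rejects the level:

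| n | Percentage rule (x/n ≥ 0.33) | Count rule (x ≥ 2) |
|---|---|---|
| 3 | 1 (1/3 = 33.3%) | 2 |
| 4 | 2 (1/4 = 25% passes) | 2 |
| 5 | 2 (1/5 = 20% passes) | 2 |
| 6 | 2 (1/6 = 16.7% passes; 2/6 = 33.3% fails) | 2 |

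The rules disagree at one outcome only, 1 of 3. Within these cohort sizes, the percentage threshold adds no rejection to the count rule except the one that contradicts the expansion bullet.

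**2. How often it would matter.** The documents give no DLT rate. I assume independent DLTs with probability p of 5%, 10%, 20% or 30%, write q = 1 − p, and take the expansion as a full three subjects.

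- Probability of exactly 1 of 3: 3pq².
- Probability that a level passes with expansion (0 of 3, or 1 of 3 followed by 0 of 3): q³ + 3pq² × q³.
- Probability that a level passes under the literal percentage rule (0 of 3 only): q³.

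For example, at p = 0.10, q³ = 0.9³ = 0.729 and 3pq² = 3 × 0.1 × 0.81 = 0.243. The pass probability with expansion is 0.729 + 0.243 × 0.729 = 0.906, and the difference is 0.177.

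| p | P(exactly 1 of 3) | Pass, expansion rule | Pass, literal 33% rule | Difference |
|---|---|---|---|---|
| 0.05 | 0.135 | 0.973 | 0.857 | 0.116 |
| 0.10 | 0.243 | 0.906 | 0.729 | 0.177 |
| 0.20 | 0.384 | 0.709 | 0.512 | 0.197 |
| 0.30 | 0.441 | 0.494 | 0.343 | 0.151 |

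These figures are for a single level and leave out the re-escalation bullets in 3.2.

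**The case against.** The strongest reply is that the documents already answer the question. The rule for 1 of 3 is specific and stated twice, the design is repeatedly called a standard 3+3, and a specific rule normally overrides a general percentage. The percentage bullet sits beside the MTD bullets and speaks of six patients, so it was probably written with completed cohorts in mind, where it agrees with the count rule. The list is introduced as guidelines, three people make the decision, and the error would be cautious. All of this stands as evidence of intent and limits the practical risk. It does not make the text consistent: the six-patient condition does not reach the level being rejected, and Section 10.5 treats the contents of 3.2 as rules. The re-escalation bullets help only when toxicity at the lower level is Grade 2 or less, or when attribution is uncertain.

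A second reply is that the percentage bullet protects outside cohorts of three to six. Above six subjects the count rule is silent. But 3.2 governs escalation levels, which Table 3.1 caps at six, and Section 3.1 defines DLT evaluability for the escalation cohort only. Below three, 2 of 2 would escape a count rule written for three to six; wording it as up to six closes that gap.

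A third reply is that the MTD proviso in 3.2, which tolerates up to 2 of 6, conflicts with the count rule. That is true, but it is a separate defect and is not addressed here.

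**Conclusion.** The concern holds. As written, the percentage bullet rejects a level at 1 of 3, and an earlier bullet in the same section and the synopsis expand it. The conflict is confined to that one count, and the intended reading is expansion. It does not follow that the team would reject at 1 of 3 in practice.

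If the literal reading were applied, the chance that a level passes would fall by 0.12 to 0.20 at true DLT rates of 5% to 30%. Those rates are assumed, so the figures illustrate the size of the effect and are not the trial's expected operating characteristics. The risk is early stopping and too low an MTD, not exposure to a rejected dose. This should be fixed, because it concerns the central decision of the escalation and the correction is small.

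**What to change.** In Section 3.2, replace the percentage threshold with two or more DLTs in up to six subjects; this is the better option because it also covers 2 of 2. Alternatively, limit the bullet to a level with six evaluable subjects. Either way, keep the sentence that makes the level below the MTD. State the verdicts once:

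- 1 of 3: expand to six.
- 1 of 6: escalation may continue.
- Two or more of three to six: unacceptable.

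The synopsis rule for 1 of 3 and Section 10.5 need no change. Within cohorts of three to six no protection is lost, because the rules differ only at 1 of 3.

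The cost is one line of wording, plus the supporting company's review and the IRB approval that Section 11.2 requires for a protocol revision. No subjects are added beyond the three to six per level in Table 3.1.
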